1.1 Synopsis

Title of the study: Phase I clinical study to evaluate the safety and tolerability of PRO-185 ophthalmic solution applied in clinically healthy subjects	
Study number: SOPH185-0521/I	Creation date: 05/17/2021
Protocol version: 2.0	Version date: 27/07/2022
Therapeutic indication: Ocular vasoconstrictor	Use: Conjunctival hyperemia
Estimated duration of the study (from the first visit of the first patient to the preparation of the final report) : 5 months	Clinical development phase: Yo
Goals: Main objective: 
• To evaluate the safety and tolerability of PRO-185 ophthalmic solution in ophthalmologically and clinically healthy subjects. Specific objectives: 
• To evaluate the safety of PRO-185 ophthalmic solution by measuring the incidence of subjects experiencing an increase of >5 mmHg in intraocular pressure 20 minutes after application compared to the initial value.• To evaluate the safety of PRO-185 ophthalmic solution by measuring the incidence of subjects experiencing a heart rate variation of >15 beats per minute 20 minutes after application.• To evaluate the safety of PRO-185 ophthalmic solution by measuring the incidence of subjects with an increase in systolic blood pressure of >15 mmHg or >10 mmHg in diastolic blood pressure 20 minutes after application.	

- To assess tolerability by the incidence of grade 3 and 4 conjunctival hyperemia.
- To assess tolerability by the incidence of pharmacological mydriasis.
- Evaluate tolerability by the incidence of expected and unexpected adverse events.

Hypothesis :

H_0 = PRO-185 ophthalmic solution is safe and tolerable for ophthalmic use, as it occurred in 20% or less of subjects with any of the following adverse events: increased intraocular pressure (IOP >5 mmHg), heart rate variation (>15 bpm), increased systemic blood pressure [>15 mmHg systolic (SBP) or >10 mmHg diastolic (DBP)], pharmacological mydriasis, or grade 3 and 4 conjunctival hyperemia.

$$H_0: p - p_0 \leq \delta$$

H_1 = PRO-185 ophthalmic solution is not safe or tolerable for ophthalmic use because more than 20% of subjects experienced any of the following adverse events: increased IOP (>5 mmHg), heart rate variation (>15 bpm), increased systemic blood pressure [>15 mmHg systolic (SBP) or >10 mmHg diastolic (DBP)], pharmacological mydriasis, or grade 3 and 4 conjunctival hyperemia.

$$H_1: p - p_0 > \delta$$

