- Present unresolved injuries or traumas at the time of entering the study.
- Have a history of any type of eye surgery.
- Having undergone non-ophthalmological surgical procedures in the last 3 months.

Research Product (RP):

- PRO-185. Naphazoline 0.03% and hypromellose 0.2%. Solución oftálmica. Laboratorios Sophia, S.A. de C. V., Zapopan, Jalisco, Mexico.
- Dosage : 1 drop 4 times a day in both eyes (AO).
- Route of administration: Ophthalmic.

Duration of treatment:	Subject's duration in the study:
8 days	10 days

Evaluation criteria:**Primary outcome variables**

- Intraocular pressure
- Heart rate
- Systemic blood pressure
- Pupillary diameter
- Conjunctival hyperemia

[figure not shown]
Secondary outcome variables:

- Best corrected visual acuity
- Changes in ocular surface staining
- Incidence of chemosis
- Incidence of expected adverse events
- Incidence of unexpected adverse events

Statistical methodology

Statistical analysis will be performed using specialized statistical software (SPSS statistical package, available version, or R software). Quantitative variables will be expressed as measures of central tendency: mean, median, standard deviation, and ranges. Qualitative variables will be presented as frequencies and percentages. Statistical analysis to rule out differences will be performed using nonparametric statistics, using the Wilcoxon signed-rank test for one sample, for quantitative variables. Analysis between qualitative variables will be performed using the binomial X² (Chi-square) test or Fisher's Exact test (when applicable). An alpha (α) ≤ 0.05 will be considered significant .

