4.1 General description of the study

Phase I clinical study, controlled, non-comparative, open, single-center

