7.3 Treatment assignment

- This is an open-label, comparative study. All patients will receive the same treatment.

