7.4.2 Secondary outcome variables

- Best corrected visual acuity (BCVA).
- Changes in ocular surface staining.
- Incidence of chemosis.
- Incidence of expected adverse events.
- Incidence of unexpected adverse events.

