	appearance is observed secondary to vasodilation of the vessels of the conjunctiva of variable intensity.	the Efron scale (see appendix 16.1)		3= Moderate 4= Severe	
Changes in the AVMC	Spatial visual acuity is the ability to distinguish separate elements of an object and identify them as a whole. It is quantified as the minimum angle of separation (located at the nodal point of the eye) between two objects that allows them to be perceived as separate objects.	Snellen chart	Continuous quantitative	0.6 to 2.0	Wilcoxon one-sample signed-rank test
Changes in ocular surface staining	Detection of epithelial defects in the cornea and conjunctiva.	Direct observation with a slit lamp will be graded according to the SICCA (see annex 16.2) [34].	Discrete quantitative	0 to 12	Wilcoxon one-sample signed-rank test
Incidence of Chemosis	It is conjunctival edema, the result of an inflammatory reaction. It is classified as present or absent.	The evaluator will use a narrow beam of light at 60° and measure whether the conjunctiva separates by $\geq 1/3$ of the entire eyelid opening or if it extends beyond the gray line.	Nominal qualitative	Present / Absent	Binomial χ^2

Variable	Conceptual Definition	Operational Definition	Type of measurement	Reference value	Statistical test
Incidence of AE	Any adverse medical event that occurs in a patient or clinical research subject who has been administered a pharmaceutical product and that does not necessarily have a causal relationship with this treatment [35].	All AEs will be reported (according to the protocol) and not only those in which the PI suspects a causal relationship with the treatments.	• Discrete quantitative • Nominal qualitative	• Incidence • Seriousness (gravity) • Causality	Binomial χ^2
Respiratory rate	The process involves inspiration and expiration, diffusion of oxygen from the pulmonary alveoli to the blood and carbon dioxide from the blood to the alveoli, and the transport of oxygen to body tissues and organs.	RR is the number of breaths a person takes per minute at rest.	Discrete quantitative	12 – 16 rpm	Wilcoxon one-sample signed-rank test
Body temperature	A clinical parameter that reflects the physiological state of the body. It is the balance between heat production and heat loss.	Degree of heat or cold, expressed in terms of a specific scale, using a thermometer.	Continuous quantitative	36.7 – 37.4°C	Wilcoxon one-sample signed-rank test

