10.3.2.2 Analysis for secondary variables

For the analysis of these variables, the same primary analysis will be performed as long as the necessary measurements are available.

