## PRO-185 (naphazoline hydrochloride 0.03%)

Variable	Conceptual Definition	Operational Definition	Type of measurement	Reference value	Statistical test
					Mann's Whitney*
Incidence of Chemosis	It is conjunctival edema, the result of an inflammatory reaction. It is classified as present or absent.	The evaluator will use a narrow beam of light at 60° and measure whether the conjunctiva separates by $\geq 1/3$ of the entire eyelid opening or if it extends beyond the gray line.	Nominal qualitative	Present / Absent	McNemar
Incidence of EA	Any adverse medical event that occurs in a patient or clinical research subject who has been administered a pharmaceutical product and that does not necessarily have a causal relationship with it.	All AEs will be reported (according to the protocol) and not only those where the PI suspects a causal relationship with the treatment [13].	• Quantitative discreet • Nominal qualitative	• Incidence • Seriousness (gravity) • Causality	• Mann Whitney • X 2 of Pearson or Exact of Fisher*
Frequency respiratory	The process involves inspiration and expiration, diffusion of oxygen from the pulmonary alveoli to the blood and carbon dioxide from the blood to the alveoli, and the transport of oxygen to body tissues and organs.	The FR is the amount of breaths a person takes per minute at rest.	Quantitative discreet	12 – 16 rpm	Kolmogorov-Smirnov or U Mann's Whitney*
Body temperature	clinical parameter that reflects the physiological state of the organism. It is the balance between heat produced and heat lost.	Degree of heat or cold, expressed in terms of a specific scale, using a thermometer.	Quantitative continues	36.7 – 37.4°C	Kolmogorov-Smirnov or U Mann's Whitney*

Abbreviations: BCVA, best-corrected visual acuity; AE, adverse event; HR, heart rate; RR, respiratory rate; PI, principal investigator; bpm, beats per minute; DBP, diastolic blood pressure; SBP, systolic blood pressure; IOP, intraocular pressure; rpm, breaths per minute; TF, fluorescein staining; TVL, lissamine green staining; X 2 Chi-square.

\*When applicable.

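### Adverse-event incidence, one of three tolerability objectives, is assigned tests with no stated reference rate or that compare groups, and no confidence interval is planned

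*Protocol*

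**What the plan says.** **Objective and rank.** The last specific objective in Protocol 1.1 and 3.1.2 is to "Evaluate tolerability by the incidence of expected and unexpected adverse events". The other two tolerability objectives are grade 3 and 4 conjunctival hyperemia and pharmacological mydriasis. Protocol 7.4.2 lists AE incidence, including "Incidence of unexpected adverse events", as a secondary outcome.

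**Test in the protocol.** The synopsis rule is general: "Analysis between qualitative variables will be performed using the binomial" chi-square, or Fisher's exact test where applicable, at alpha 0.05. Table iii (7.4.4) applies it to this outcome: the AE-incidence row names the binomial chi-square, and its reference-value cell reads "Incidence • Seriousness (gravity) • Causality", with no number. Section 10.3.2.2 adds only "For the analysis of these variables, the same primary analysis will be performed as long as the necessary measurements are available".

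**Test in the SAP.** The AE-incidence row of SAP Table 2 names Mann-Whitney for the count and "X 2 of Pearson or Exact of Fisher" for the categorical form. SAP 6.2.2 repeats the rule of Protocol 10.3.2.2.

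**Design.** Protocol 4.1 describes a "Phase I clinical study, controlled, non-comparative, open, single-center" trial. Protocol 7.3 calls the study comparative but goes on: "All patients will receive the same treatment". SAP 3.5 calls it open and non-comparative. There is one arm.

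**Rates.** Protocol 10.1.1 takes 20% as the AE incidence for the sample size; SAP 4.1 takes 10%. The limits in Protocol 3.2 (20%) and SAP 3.2 (10%) apply to five named events: rises in intraocular pressure, heart-rate change, rises in blood pressure, mydriasis and grade 3 and 4 hyperemia.

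**Output.** Protocol 1.1 and 10.3.1 and SAP 6.1 plan frequencies, proportions or percentages for categorical variables. Neither document plans a confidence interval. The only ones mentioned are error bars in the charts of the rabbit study.

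**The concern.** A one-sample binomial test asks whether an incidence differs from a stated value. With no value stated for this outcome, the p-value has no defined hypothesis. Pearson chi-square, Fisher and Mann-Whitney ask whether two independent groups differ. With everyone on the same product there are no two groups whose contrast is the AE incidence. A before/after reading does not help, because these tests ignore pairing and neither document assigns a paired test to AE incidence.

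Two things are at stake. First, two analysts who follow the protocol and the SAP respectively would run different tests, and those who borrow different reference rates could reach opposite conclusions from the same count. Second, without an interval the report would not show what 22 subjects can exclude. That upper limit is the main thing a small AE table can tell the reader, and Protocol 2.3 and 2.4.1 say there is no earlier clinical study of this formulation.

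**Working it through.** **1. Sample size on which precision depends.** Protocol 10.1.2 gives reference p0 = 0.20, margin 0.10, z = 1.96 and power 0.80, but never states the expected p. Assuming p = 0.10, from the SAP's 10%, and variance p(1 - p):

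n = 0.10 × 0.90 × [(1.960 + 0.842) / (0.10 - 0.20 - 0.10)]² = 17.66, rounded up to 18.

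18 × 1.2 = 21.6, rounded up to 22. The stated 18 and 22 are reproduced. The safety population is everyone who received at least one dose (Protocol 10.3.2.1), so N for AE incidence can be 22.

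**2. How the answer depends on the reference rate.** Take 6 of 22 subjects with an AE (27.3%) as an illustration, using the exact binomial test. The two-sided p adds every outcome no more likely than the one observed.

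- Against 10%: P(X ≥ 6) = 0.018. No low count is as improbable as 6, so the two-sided p is also 0.018.
- Against 20%: P(X ≥ 6) = 0.267 and P(X ≤ 2) = 0.154, so the two-sided p = 0.42.

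One-sided, the values are 0.018 and 0.27. The data are the same; the SAP's rate gives a significant result and the protocol's does not.

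**3. What a test against 20% could show, if 20% were adopted.** With N = 22 and one-sided 0.05:

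- Below 20%: P(X ≤ 1) = 0.048, but P(X ≤ 2) = 0.154. Only 0 or 1 subject with an AE would show it.
- Above 20%: P(X ≥ 9) = 0.020, but P(X ≥ 8) = 0.056. It takes 9 or more.

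Counts from 2 to 8 would be non-significant in both directions and exclude little.

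**4. What an interval would show.** Exact (Clopper-Pearson) two-sided 95% limits. For zero events the upper limit is 1 - 0.025^(1/N); for N = 22 this is 1 - 0.8456 = 0.154.

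| Subjects with AE / N | Observed | 95% interval |
|---|---|---|
| 0/22 | 0% | 0 to 15.4% |
| 1/22 | 4.5% | 0.1 to 22.8% |
| 3/22 | 13.6% | 2.9 to 34.9% |
| 6/22 | 27.3% | 10.7 to 50.2% |
| 0/18 | 0% | 0 to 18.5% |

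An AE with a true incidence of 5% would be missed entirely in 22 subjects with probability 0.95^22 = 0.324, about one chance in three.

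**The case against.** Four points can fairly be made on the other side.

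- **The tests may have another use.** Protocol Table vi and SAP Table 3 cross AE incidence with other variables in 2×2 tables and multivariate analyses, and SAP Table 2 marks Pearson or Fisher as applying only where applicable. Groups need not be arms: subjects with and without an AE could be compared on another variable. This stands, so it would be wrong to infer that these tests have no conceivable role. But such a comparison concerns association and does not answer how often AEs occur, which is the objective.

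- **A reference can be inferred.** Protocol 10.1.1 gives a 20% AE rate, and 10.3.2.2 carries the primary analysis over to secondary variables. A reader might conclude that the analyst is entirely free to choose the null after seeing the data; the documents do not support that, because they offer 20% or 10%. But both are planning inputs, they disagree, and neither is assigned to this test. Nor is 20% an obvious benchmark for AEs overall: in the earlier study of a stronger formulation (Protocol 2.3.3), 86% of healthy volunteers reported burning, which Protocol 7.4.5.9 lists as a possible AE here.

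- **The outcome is secondary.** The decision rule in Protocol 3.2 rests on the five named events. This stands, and it limits the importance of the point.

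- **The descriptive result is planned.** Counts and percentages will be shown, all AEs are recorded regardless of causality, and a reader could compute an interval. No text says that a non-significant result will be read as absence of a problem. That stands too. What is missing is the interval in the plan, beside a test that cannot replace it.

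**Conclusion.** The point holds in a limited form. For AE incidence the protocol names a one-sample test without a reference value, the SAP names tests for independent groups, and neither document plans an interval. The practical size is a p-value that moves from 0.42 to 0.018 for 6 of 22 depending on which document's planning rate is borrowed, and unreported upper limits of 15.4% for no events and 22.8% for one.

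A reader might infer that the trial's overall safety and tolerability decision rests on an undefined test. The documents do not support that: AE incidence is one of three tolerability objectives and does not enter the five-event hypothesis, which has its own stated threshold in each document.

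The figures assume 22 subjects in the safety population, one binary outcome per subject, and exact binomial methods. The event counts are illustrations, not predictions. The change should be made because it is cheap and gives a better answer to the objective, but the trial does not depend on it.

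**What to change.** - **Protocol Table iii and SAP Table 2:** remove the significance tests from the rows for AE incidence, including seriousness and causality. This also removes the conflict between the two documents on this outcome.
- **Protocol 10.3.2.2 and SAP 6.2.2:** exempt AE incidence from the rule that secondary variables follow the primary analysis. State instead that the number of subjects with at least one AE will be reported as n/N (%) with an exact (Clopper-Pearson) two-sided 95% confidence interval, for all, expected, unexpected and product-related AEs. Intervals for each individual AE term are optional.
- **Protocol 1.1:** note in the general rule for categorical variables that AE incidence is reported this way.
- **Interpretation:** word any statement on AE incidence from the upper limit, for example that no case was seen among 22 subjects and that the 95% interval extends to 15.4%.
- **Leave the five-event hypothesis out of this change.**

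The cost is wording in two documents, with no new subjects, visits or data. The drawback for the sponsor is that a zero or low count will appear with an upper limit that reads less favourably than the bare percentage.

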1.2 Study diagram

CONFIDENTIAL

1.3 Subject's activity schedule

Procedures	Baseline visit		Visit 1		Visit 2		Final visit
	Day 1		Day 3 (+1)		Day 8		Day 10 (+1)
	Pre-TP	Post -	Pre -	Post-	Pre -	Post-	Without
	TP		Tx	Tx	Tx	Tx	treatment
FCI Signature	X						
Medical record	X						
Eligibility criteria	X						
Subject code assignment	X						
Adverse events	X	X	X	X	X	X	X
Heart rate	X	X	X	X	X	X	X
Respiratory rate	X		X		X		X
Blood pressure	X	X	X	X	X	X	X
Temperature (°C)	X		X		X		X
Urine pregnancy test	X						X
AVMC	X		X		X		X
Anterior segment evaluation	X	X	X	X	X	X	X
Pupillary diameter measurement	X	X	X	X	X	X	X
Eye stains	X	X	X	X	X	X	X
Intraocular pressure	X	X	X	X	X	X	X
Gonioscopy	X						
Pharmacological mydriasis (phenylephrine/tropicamide)	X						
Evaluation of the posterior segment	X		X		X		X
Application of PRO-185 during a visit			X		X		
Delivery of material for the subject		X					
Delivery of the study medication		X					

Procedures	Baseline visit		Visit 1		Visit 2		Final visit
	Day 1		Day 3 (+1)		Day 8		Day 10 (+1)
	Pre-TP	Post -	Pre -	Post-	Pre -	Post-	Without
	TP	Tx	Tx	Tx	Tx	Tx	treatment
Evaluation of concomitant medications	X		X		X		X
Adherence assessment			X		X		
Return of study medication						X	
Withdrawal from the subject's diary						X	

PRE-TP: prior to application of 0.8% tropicamide and 5% phenylephrine ophthalmic solution (TP Ofteno[®]), indicates that the checks will be performed prior to pharmacological mydriasis. Post-TP: post application of the TP Ofteno[®] solution, indicates that the checks will be performed with pharmacological mydriasis. Pre- Tx : pretreatment, indicates the checks to be performed before the application of the investigational medicinal product. Post-Tx : post-treatment, indicates the evaluations to be performed within 20-40 minutes after the application of the investigational medicinal product. ICF: informed consent form. BCVA: best corrected visual acuity.

2. Introduction and background

2.1 Theoretical framework

2.1.1 The red eye

Red eye is a cardinal sign of ocular inflammation, a very common presentation, and one of the most frequent ophthalmologic conditions in primary care. As a nonspecific sign of inflammation, its etiology is highly varied and can range from disorders that do not threaten vision (such as some infectious conjunctivitis, allergic and irritant conjunctivitis, and blepharitis, etc.) to diseases that are potentially harmful to the organ and its function (such as uveitis, acute angle-closure glaucoma, endophthalmitis, etc.). [1]

Through the patient's medical history and examination, the etiology of the red eye can be diagnosed and the treatment to be followed determined accordingly. [1] [2]

In self-limiting conditions, such as viral and irritant conjunctivitis, management is based on symptomatic measures focused on reducing conjunctival hyperemia and itching, relieving the patient's discomfort during the illness. This treatment may include cold compresses, decongestants, and lubricants. In some conditions, such as allergic and bacterial conjunctivitis, in addition to etiological treatment with antihistamines or antibiotics, respectively, symptomatic support measures are also recommended. [1] [2] [3] [4]

Synthetic adrenergic agonists such as phenylephrine, naphazoline, oxymetazoline, and tetrahydrozoline are available as ocular decongestants. After topical application, they produce vasoconstriction at concentrations that do not cause mydriasis. These agents provide symptomatic therapy, as they have no effect on the conjunctival response to antigen. [5]

Red eye is a common problem in the general population, accounting for approximately 15% of ophthalmology consultations and almost 6% of general practitioner visits. Symptoms and signs that may accompany red eye include irritation, itching, discharge, tearing, and eye pain. [6]

The first thing to evaluate in patients with red eye is whether it is caused by a serious eye disease. To rule out a serious ophthalmologic disorder, it is important to inquire about the patient's absence of significant eye pain, blurred vision, and photophobia. [7]

Ocular biomicroscopy is a useful tool that can diagnose the causes of more than 90% of conditions associated with red eye. During the examination, it is important to take an adequate history, detailing the onset of the red eye, the duration of its onset, whether the condition is unilateral or bilateral, associated symptoms, ocular and systemic diseases, use of topical and systemic medications, history of trauma, and contact lens use. [8] [9]

The examination should include a visual inspection of the periocular region, adnexa, ocular surface, and anterior chamber. This allows for differentiation of hyperemia in conditions related to eyelid

abnormalities, peripheral (predominantly in the fornix), perikeratic (greater intensity in the scleral-corneal limbus), and localized conditions. Alterations in corneal transparency or elements in the anterior chamber, such as hyphema or hypopyon, should be sought. Fluorescein staining can identify de-epithelialized regions. [9] Table 2 summarizes the main causes of red eye, according to the predominant location of the conjunctival hyperemia.

Table ii. Main causes of red eye

Red eye of palpebral or periocular origin	Diffuse superficial red eye

 Blepharitis Chalazion Stye Orbital cellulitis Dacryocystitis 	
 Infectious conjunctivitis Allergic conjunctivitis Dry eye syndrome
Perikeratic red eye of intraocular origin	Localized red eye

 Keratitis, corneal erosion Uveitis Glaucoma 	
 Subconjunctival hemorrhage Pterygium Episcleritis Scleritis

2. 1.2 Pathophysiology of red eye

Red eye results from vasodilation of conjunctival blood vessels. Vascular tone in mammals is regulated by the activity of adrenergic receptors found in vascular smooth muscle, vascular endothelium, and nerve cell terminals. The contractile activity of smooth muscle cells alters blood vessel diameter. Stimulation of α_1 and α_2 adrenergic receptors causes vasoconstriction of vascular smooth muscle; meanwhile, stimulation of β adrenergic receptors causes vasodilation. Additionally, stimulation of α_1 , α_2 , and/or β adrenergic receptors on vascular endothelium will cause vasodilation, possibly by increasing nitric oxide. Basal vascular tone is governed by norepinephrine-mediated vasoconstrictor and vasodilator activity, and red eye occurs when vasodilation predominates. [10]

By analogy, the vasoactive effect of active ingredients with adrenergic agonist activity will depend on the balance between vasoconstrictor and vasodilator activity. Anatomical differences in the

distribution of α_1 and α_2 adrenergic receptors are important, since α_1 receptors are found in veins and arteries, while α_2 receptors predominate in veins. Consequently, the effects of the active ingredients will depend on the receptors they activate. [10]

